TITLE: Analgesic efficacy of orally administered VTS-K (liquid oral ketamine taken simultaneously with VTS-Aspirin) for pain management of adult ED patients presenting to the ED with acute musculoskeletal pain

NCT #:

Document Date: October 19, 2020

TITLE: Analgesic efficacy of orally administered VTS-K (liquid oral ketamine taken simultaneously with VTS-Aspirin) for pain management of adult ED patients presenting to the ED with acute musculoskeletal pain

INTRODUCTION

Acute Pain is one of the most frequent chief complain and the main reason for visiting the Emergency Department (ED). The acute pain in the ED is largely prevalent across the country with recent literature demonstrating that 61-91% of patients are admitted to the ED due to a variety of acute painful syndromes.(1) Musculoskeletal pain (MSK) affects one out of three adults and it is the most common source of serious long term pain and physical disability (2). Furthermore, studies have demonstrated that the frequency for analgesia for adults who received treatment for musculoskeletal pain in the ED is between 11-29% (3). To complicate the issue of MSK pain management even further, the opioid epidemic spanning over 20 years in the USA and claiming over 400,000 deaths from unintentional prescription opioid overdose, has forced health care systems and hospitals across the nation to reduce the reliance on opioid analgesics and embrace the utility of non-opioid analgesia. Several classes of non-opioid analgesics such as Acetaminophen, NSAID's (aspirin, ibuprofen, diclofenac) and Ketamine have gained great deal of attention as viable alternatives to opioids in management of acute MSK pain in the ED (4-8).

BACKGROUND AND SIGNIFICANCE

The CERTA concept is based on our improved understanding of neurobiological aspect of pain with a shift from symptom-based approach to pain to a mechanistic approach. This targeted, patient-focused analgesic approach allows for a broader utilization of combinations of non-opioid analgesics. These synergistic combinations of different classes of analgesics acting on different target sites have a potential to result in greater analgesia, reduced dose of each individual medication and shorter length of stay. In addition, this concept will allow us to administer non-opioid analgesic modalities as first-line therapies in the ED and utilize opioids as rescue analgesics (9).

A combination of ketamine and aspirin for the treatment of acute MSK pain in the ED would confer multimodal analgesia, with the contributions of aspirin and ketamine to an opioid sparing effect. Research on this multimodal approach is sparse, but the minimal empirical evidence supports a clinical benefit to patients in a post orthopedic surgery setting, both in short term and long term. Remerand et al. evaluated the effect of ketamine in combination with multimodal

analgesia, including non-steroidal anti-inflammatory drugs, like aspirin, on acute and chronic postoperative pain following total hip arthroplasty (THA)(10). All patients were treated perioperatively with NSAIDs, and then randomized to a postoperative treatment of ketamine or opioids. Patients randomized to the ketamine group demonstrated decreased opioid consumption at hour 24 (19 ± 12 mg to 14 ± 13 mg, $P=0.0004$), which is indicative of the opioid sparing effect frequently seen. The ketamine patients also demonstrated improved rehabilitation. From Day 30 to Day 180, the patients randomized to a treatment of ketamine required less assistance walking (56% to 31%, $P=0.0035$), and a smaller proportion of the ketamine-treated patients experienced persistent pain at rest in the operated hip ($P=0.008$). At Day 180, 21% of the control group patients experienced pain at rest, as compared to the ketamine group, in which only 8% experienced this pain ($P=0.036$).

Ketamine is a non-competitive N-methyl-D-aspartate (NMDA)/glutamate receptor complex antagonist that decreases pain by diminishing central sensitization, hyperalgesia, and “wind-up” phenomenon at the level of the spinal cord (dorsal ganglion) and central nervous system (11). Ketamine administration in sub-dissociative doses (SDK) of 0.1-0.3 mg/kg in pre-hospital settings and in the ED results in effective pain relief in patients with acute traumatic and non-traumatic pain, chronic non-cancer and cancer pain, and in patients with opioid-tolerant pain by virtue of providing anti-hyperalgesia, anti-allodynia, and anti-tolerance (12-14). Two commonly utilized routes of SDK administration in the ED include an intravenous route (intravenous push dose or short infusion) and intranasal route (15-20).

Internationally, oral ketamine wafers/tablets have been used as an alternative to the IV form but are currently unavailable in the United States. Despite the fact that ketamine undergoes extensive first-pass metabolism with an oral bioavailability of approximately 16%, a relatively low orally administered dose of ketamine was required to achieve patient comfort in the study of patients undergoing burn wound dressing changes.(21,22) Oral administration results in decreased ketamine and increased norketamine concentrations in serum.²⁰ Consequently, oral ketamine’s first-pass effect from hepatic metabolism of ketamine to norketamine may help maintain analgesic potency while simultaneously decreasing side effects when compared to the IV form.(23)

Aspirin is a prototype of non-steroidal anti-inflammatory drugs (NSAIDs), and member of the family of salicylates that have in common salicylic acid as the active agent. The pharmacological properties of aspirin are similar to those of salicylates, but also to the biological actions attributed to salicylate itself, and it has other independent effects due to its reactive acetate group. Both components, salicylate and acetate groups, are biologically active and act independently of each other at different sites (24). Aspirin is a safe and well-understood non-steroidal anti-inflammatory drug (NSAID). It has certain and clinically accepted analgesic properties. It is a non-selective and irreversible NSAID that inhibits an activity of both cyclooxygenase-1 and 2 and blocks the synthesis of prostaglandins and thromboxanes. (25)

Vitalis Pharmaceuticals (New York, NY) has developed a proprietary formulation of aspirin, VTS-Aspirin that may deliver faster and stronger pain reduction than traditional aspirin. Preliminary research indicates that combinations of VTS-Aspirin with analgesics may confer greater benefit in pain management than some current standards of care (26).

An oral combination drug of VTS-Aspirin and ketamine (VTS-K) would facilitate the shift from IV opioids to a non-IV therapy for patients presenting to the ED with acute MSK pain. This formulation has a potential to provide effective analgesia in the ED with reduced side effects. VTS-K's proprietary oral formulation of established, safe, and well-understood APIs, makes it uniquely appropriate for use in the ED. VTS-K is administered orally, which is suitable for resource-poor environments in which the healthcare setting may be inadequate as well as suitable to improve the throughput of ED Patients by reducing their length of stay. This is especially pertinent given the alternative of IV opioids for pain management of acute MSK pain, which requires both clinical monitoring and equipment, whereas VTS-K promotes weaning off opioids, alleviating the resource consumption.

STUDY OBJECTIVES

To evaluate analgesic efficacy of orally administered VTS-K (liquid oral ketamine taken simultaneously with VTS-Aspirin and oral ketamine (in a liquid form)) for pain management of adult ED patients presenting to the ED with acute musculoskeletal pain

HYPOTHESIS

In our pilot study we hypothesize that the VTS-K combination will result in analgesia with a change in pain score at least of 1.3 points on NRS. The primary outcome of this trial is the reduction in participant's pain scores at 60 minutes post medication administration.

STUDY DESIGN

Subjects: Patients 18 years of age and older presenting to the ED with acute musculoskeletal painful conditions (traumatic and non-traumatic) with an initial pain score of 5 or more on a standard 11- point (0 to 10) numeric rating scale and requiring oral analgesia as determined by the treating attending physician. Patients' screening and enrollment will be performed by study investigators and research assistants. All patients will be enrolled at various times of the day when study investigators will be available for patient enrollment and an ED pharmacist will be available for medication preparation

Eligibility Criteria: Patients 18 years of age and older presenting to the ED with acute musculoskeletal painful conditions (traumatic and non-traumatic) with an initial pain score of 5 on a standard 11- point (0 to 10) numeric rating scale. Patients will have to be awake, alert, and oriented to person, place, and time, and will be able to demonstrate understanding of the informed consent process and content. Patients also will have to demonstrate ability to verbalize the nature of any adverse effects they might experience as well as to express their pain severity by using the NRS.

Exclusion Criteria: Patients with altered mental status, allergy to aspirin and ketamine, pregnant patients, unstable vital signs (systolic blood pressure <90 or >180 mm Hg, pulse rate <50 or >150 beats/min, and respiration rate <10 or >30 breaths/min), inability to provide consent, consumption of Aspirin or NSAID's within 6 hours of arrival to the ED, active PUD, history of GI Hemorrhage,

history of renal and hepatic insufficiency, past medical history of alcohol or drug abuse, or schizophrenia.

Design: This is a prospective observational pilot trial evaluating analgesic efficacy and safety of VTS-K in adult patients presenting to the ED of Maimonides Medical Center with acute musculoskeletal painful conditions. Upon meeting the eligibility criteria, patients will be offered to participate in the study.

Data Collection Procedures: Each patient will be approached by a study investigator for acquisition of written informed consent and Health Insurance Portability and Accountability Act authorization after being evaluated by the treating emergency physician and determined to meet study eligibility criteria. When English will not be the participant's primary language, a language-appropriate consent form will be used and non-investigator, hospital-employed, trained interpreters or licensed telephone interpreter will assist in acquisition of informed consent. Baseline pain score will be determined with an 11-point numeric rating scale (0 to 10), described to the patient as "no pain" being 0 and "the worst pain imaginable" being 10. A study investigator will record the patient's body weight and baseline vital signs.

The on-duty ED pharmacist will prepare an oral dose of ketamine by using a formulary for parenteral use. The oral dosing regimen of ketamine is 0.5 mg/kg that will be placed in the syringe or a medication cup. The research associate will deliver both medications (VTS-Aspirin and Oral Ketamine) to the patient. Study investigators will record pain scores and adverse effects at 15, 30, 60, and 90 minutes. If patients reported a pain numeric rating scale score of 5 or greater and requested additional pain relief, an oral immediate release morphine tablet of 7.5 mg will be given

All data will be recorded on data collection sheets, including patients' sex, demographics, medical history, and vital signs, and entered into SPSS (version 24.0; IBM Corp) by the research manager. Confirmation of written consent acquisition for all participants, and statistical analyses will be conducted by the statistician, who will work independently of any data collection.

Patients will be closely monitored for adverse effects during the entire study period (up to 90 minutes) by study investigators. Common adverse effects that are associated with oral ketamine are feeling of unreality, dizziness, nausea, vomiting, and sedation. Common adverse effects are associated with VTS-Aspirin are nausea, dyspepsia, epigastric discomfort.

Data Analysis: Data analyses will include frequency distributions and independent-sample t-test to assess differences in pain scores at the various intervals.

Mixed-model linear regression will be used to compare changes in pain numeric rating scale across time points. For categorical outcomes (eg, complete resolution of pain), a χ^2 or Fisher's exact test will be used to compare outcomes at 60 minutes. Based on the validation of a verbally administered rating scale of acute pain in the ED and the comparison of verbal and visual pain scales, we will use a primary outcome consisting of a minimal clinically meaningful difference of 1.3 between three groups at the 60-minute pain assessment.^{28,29}

Sample Size: Assuming a minimal clinically meaningful difference of 1.3 in change of pain score from the baseline until 60 minutes, given a standard deviation of 3.0, with a one-side 97.5%

confidence interval, we will need 21 subjects for this pilot trial. We would enroll 25 patients to account for any loss to follow-up.

References:

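### The hypothesis sets 1.3 NRS points as a floor, but the trial is sized only to place a confidence limit about 1.3 points from the mean, and no planned analysis compares the 60-minute change with 1.3

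*Combined protocol and SAP*

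**What the plan says.** The Hypothesis section of the combined protocol and SAP expects that "the VTS-K combination will result in analgesia with a change in pain score at least of 1.3 points on NRS". It then fixes the endpoint: "The primary outcome of this trial is the reduction in participant's pain scores at 60 minutes post medication administration".

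The Sample Size paragraph uses the same number. It begins "Assuming a minimal clinically meaningful difference of 1.3 in change of pain score from the baseline until 60 minutes", continues "given a standard deviation of 3.0, with a one-side 97.5" per cent confidence interval, and concludes "we will need 21 subjects for this pilot trial". It adds: "We would enroll 25 patients to account for any loss to follow-up". It gives no power, no reference value for the interval, and no rule linking the interval to the hypothesis.

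The Design paragraph describes one treated group: "This is a prospective observational pilot trial evaluating analgesic efficacy and safety of VTS-K in adult patients". The Data Analysis paragraph nevertheless lists an "independent-sample t-test to assess differences in pain scores at the various intervals", together with a mixed model over time points and χ² or Fisher tests for categorical outcomes. Its one use of 1.3 is as a difference between three groups, which the design does not contain. No listed analysis sets the 60-minute change, or a confidence limit for it, against 1.3.

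**The concern.** The number 1.3 is doing two different jobs. In the hypothesis it is a threshold that the change must reach. In the sample-size calculation it is the distance between the mean and its confidence limit. A limit that sits 1.3 points below the mean says, at an observed mean of 1.3, something about zero. It says nothing in favour of the true change being 1.3 or more. Showing that would need the lower limit itself to clear 1.3.

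Because the plan does not say what result supports the hypothesis, the rule would have to be chosen at reporting, possibly with the data in view. Two natural choices are to compare the observed mean with 1.3, or to check that the limit is above 0. Neither establishes a change of at least 1.3. At stake is a report that the reduction reached the smallest clinically meaningful size when the data are also compatible with a change close to zero.

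**Working it through.** Reductions are taken as positive throughout.

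**Inputs.** Threshold 1.3 (Hypothesis). SD 3.0, one-sided 97.5% interval, n=21 evaluable and 25 enrolled (Sample Size). One group (Design). Not stated: power, reference value, expected true mean.

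**Reproducing the plan's 21.** The one-sample precision formula is n = (z × SD/d)² = (1.96 × 3.0/1.3)² = 20.46, rounded up to 21. Other readings do not give 21:

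- one-sided 95% precision: 15
- t-based precision at 97.5%: 23
- one-sample test at one-sided 0.025, with 80% or 90% power: 42 or 56
- one-sample test at one-sided 0.05, with 80% or 90% power: 33 or 46
- two arms at one-sided 0.025, with 80% or 90% power: 84 or 112 per arm

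So 21 is a precision figure with no power term. The reference value it implies is 0.

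**What the interval gives.** SE = 3.0/√n. The half-width is 1.960 × SE by z. By t it is 2.086 × SE (20 df) or 2.064 × SE (24 df). The lower limit at an observed mean of 1.3 is 1.3 minus the half-width. The observed mean that puts the limit at 1.3 is 1.3 plus the half-width.

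| | n=21 | n=25 |
|---|---|---|
| SE | 0.655 | 0.600 |
| Half-width, z / t | 1.283 / 1.366 | 1.176 / 1.238 |
| Lower limit at observed 1.3, z / t | 0.02 / −0.07 | 0.12 / 0.06 |
| Observed mean needed for limit of 1.3, z / t | 2.58 / 2.67 | 2.48 / 2.54 |

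With a t interval and 21 patients, an observed mean of 1.3 does not exclude even zero.

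**If the observed mean were simply compared with 1.3.** This rule is assumed for illustration; the plan does not state it. P(observed mean ≥ 1.3) = 1 − Φ((1.3 − true)/SE).

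- True change 1.0: 32% (n=21), 31% (n=25)
- True change 0.65: 16% (n=21), 14% (n=25)

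**Power to exclude 0 at a true change of 1.3.** By z, Φ(1.3/SE − 1.960) is Φ(0.026) = 51% (n=21) and Φ(0.207) = 58% (n=25). By t (noncentral t) it is 47% and 55%.

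**Power to show at least 1.3.** At a true change of exactly 1.3 the lower limit clears 1.3 with probability 2.5%. The true mean needed for 80% power by z is 1.3 + (1.960 + 0.842) × SE, which is 3.13 (n=21) or 2.98 (n=25). By t, a true mean of 3.0 gives 70% (n=21) or 78% (n=25).

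The documents give no expected true mean. Over an assumed range, the n for 80% / 90% power against 1.3 is, by z:

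| Assumed true mean | n for 80% / 90% |
|---|---|
| 2.0 | 145 / 193 |
| 2.3 | 71 / 95 |
| 2.6 | 42 / 56 |
| 3.0 | 25 / 33 |
| 3.5 | 15 / 20 |

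**The case against.** The best reply is that this is a small observational pilot, that sizing a pilot for precision is ordinary, and that using a minimal meaningful difference as a planning value is an accepted choice. The objective is only to evaluate efficacy, and the primary outcome sentence carries no threshold. The harm is also inferred: the plan never says that a mean of 1.3 would count as success, and the zero reference is deduced from the formula that gives 21.

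Much of this stands. The hypothesis is not the plan's only statement about efficacy, and 21 is not an arithmetic error. The probabilities of passing an observed-mean rule illustrate one possible reading and do not describe a documented rule.

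It does not remove the point. The hypothesis puts a clinical floor on the change, and a pilot can keep its size and still say which result would allow that claim. The missing rule is part of the defect.

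A reader might also infer that the trial could never establish 1.3. The figures do not support that: an observed mean above about 2.5 to 2.7 would do so. Nor should a reader conclude that the stated size supports a test against zero. At a true change of 1.3 that test succeeds only about half the time.

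**Conclusion.** The stated claim and the stated inference do not match. The claim is a change of at least 1.3. The interval is sized so that a mean of 1.3 is just about separated from zero, and no listed analysis addresses 1.3 in the group actually studied. The affected range is observed means from 1.3 up to 2.54 (t, n=25) or 2.67 (t, n=21), or slightly less by z. Such results could be read as confirming the threshold without establishing it. A reader might infer that they *would* be read that way, but the plan states no success rule, so that is more than the documents support.

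The conclusion rests on the plan's SD of 3.0, on approximate normality of the mean, and on a zero reference inferred from the sample-size formula. A smaller SD would narrow the affected range and a larger one would widen it. The point concerns only what can be said about the size of the change from baseline. Attributing that change to VTS-K is a separate question in a one-group design that allows rescue morphine. The mismatch should be corrected before analysis, but it does not invalidate the pilot.

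**What to change.** Keep n=25.

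1. In Data Analysis, for the primary outcome, replace the independent-sample and three-group wording with a one-sample (paired) analysis: the mean reduction from baseline to 60 minutes with a t-based one-sided 97.5% lower limit.
2. State the permitted claims. Claim a change of at least 1.3 only if that limit is 1.3 or more. If the limit is above 0 but below 1.3, report a reduction from baseline with clinical meaningfulness not established.
3. As an alternative to the threshold claim, reword the hypothesis as a mean reduction greater than 0, with 1.3 as a planning value. Give the power with it (at a true 1.3, about 47% by t or 51% by z with n=21, and 55% or 58% with n=25), and do not describe the size as supporting the test without those figures.

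The cost is a few sentences in Hypothesis, Data Analysis and Sample Size, with no extra patients or data. The downside should be stated openly. Showing at least 1.3 with 80% power needs a true mean reduction of about 3.0 (n=25) or 3.1 (n=21), so the permitted claim will often be the more modest one.

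### The explicit bleeding exclusions stop at the GI tract, so a stable trauma patient on an anticoagulant or with a known bleeding disorder meets every written criterion for VTS-Aspirin

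*Combined protocol and SAP*

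**What the plan says.** Background and Significance says of aspirin: "It is a non-selective and irreversible NSAID that inhibits an activity of both cyclooxygenase-1 and 2 and blocks the synthesis of prostaglandins and thromboxanes". Study Design, under both Subjects and Eligibility Criteria, takes adults from 18 years upward with "acute musculoskeletal painful conditions (traumatic and non-traumatic" causes both included. No upper age limit is given.

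The Exclusion Criteria contain two items that name a bleeding or ulcer condition: "active PUD, history of GI Hemorrhage". The only item on recent medication is "consumption of Aspirin or NSAID's within 6 hours of arrival to the ED". The list closes with "history of renal and hepatic insufficiency, past medical history of alcohol or drug abuse, or schizophrenia". The remaining items are altered mental status, allergy to the study drugs, pregnancy, unstable vital signs and inability to consent.

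The one clinical judgement written into selection is in Subjects, where the patient must be "requiring oral analgesia as determined by the treating attending physician". Screening and enrolment are assigned to study investigators and research assistants. Under Design, a patient who meets the criteria is offered participation. For VTS-Aspirin, Data Collection Procedures states: "Common adverse effects are associated with VTS-Aspirin are nausea, dyspepsia, epigastric discomfort".

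**The concern.** The protocol already treats a history of bleeding as a reason not to enrol, but it writes that reason down for one organ system only. The mechanism it describes is not confined to the gut, and the population includes people with fresh injuries. A screener who follows the list exactly would offer VTS-Aspirin to a patient whose bleeding risk is raised for a non-GI reason. The trial is described under Design as evaluating safety as well as efficacy, and eligibility is the natural place to control a risk that can be known before the dose is given. What is at stake is the protection of individual patients. The primary endpoint and its analysis are not affected.

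**Working it through.** The plan gives no figure on this point, so the check is a reading of every criterion against one test patient.

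The test patient is an adult who fell and has shoulder pain. The pain score is 5, which satisfies both Subjects (5 or more) and Eligibility Criteria (5). Systolic pressure is 110 mm Hg and the other vital signs are in range. The patient is alert, oriented and able to consent, and the attending judges that oral analgesia is needed. The patient takes an anticoagulant or has a known bleeding disorder, and nothing else is notable.

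| Written item | Bears on bleeding? | Excludes this patient? |
|---|---|---|
| Active PUD, past GI hemorrhage | Directly, GI only | No |
| Aspirin or NSAID within 6 hours of arrival | Indirectly; names no anticoagulant or other antiplatelet drug | No |
| Renal and hepatic insufficiency | Indirectly | No |
| Systolic pressure <90 or >180, pulse <50 or >150, respiration <10 or >30 | Indirectly; could catch a patient who is already unstable | No |
| Altered mental status | Indirectly; could catch some major injury | No |
| Allergy, pregnancy, no consent, alcohol or drug abuse, schizophrenia | No explicit bleeding criterion | No |
| Attending judges oral analgesia is required | Not stated; concerns need and route | No |

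The patient passes every row. A search of the whole document finds no mention of anticoagulants, antiplatelet drugs other than aspirin and the NSAIDs, bleeding disorders, thrombocytopenia or a coagulation test. The exclusion list runs across a page break, but it reads continuously and shows no sign of blacked-out text, so the absence belongs to the plan.

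Whether the gap can be closed with information already at hand can also be read from the text. Data Collection Procedures has medical history recorded for each patient. The 6-hour rule already requires a question about recent drug intake. Each patient is seen by the treating emergency physician before being approached. A question about anticoagulants or a known bleeding disorder fits into these steps.

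**The case against.** The strongest reply is that the documents do not contradict themselves. Background and Significance gives a mechanism but never links it to bleeding, and it calls aspirin safe and well understood. That is correct: the step from thromboxane blockade to non-GI bleeding risk is the reviewer's inference, although an ordinary one. What remains is that the protocol itself accepts past hemorrhage as a ground for exclusion, and gives no reason for limiting that ground to the gut.

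A second reply is that bleeding risk is screened in other ways and that a physician sees every patient. This also stands in part. The recent-NSAID, renal, hepatic and blood-pressure items all have some bearing, and a physician might well decline such a patient. But the physician step written into the plan concerns the need for oral analgesia and the same eligibility list. Comparable risks, such as recent NSAID use and renal insufficiency, are written down and not left to judgement.

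A reader might also infer that no later step would detect a bleed, because the VTS-Aspirin effects listed are all gastrointestinal. The documents do not support this. The list is of common effects and is not closed, and adverse effects are recorded at 15, 30, 60 and 90 minutes without restriction by type.

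**Conclusion.** The point holds for the written criteria: the explicit bleeding exclusions are GI only, and no other item excludes a stable patient with an anticoagulant or a known bleeding disorder. It rests on the text as it stands and on the inference from mechanism to bleeding risk described above.

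Two stronger readings should not be drawn. First, a reader might infer that the safety result will look falsely favourable because observation ends at 90 minutes. That is a question of follow-up length. A change in eligibility would not alter it, and the documents give no event rate from which to argue it.

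Second, a reader might want a count of patients exposed. The expected number among 25 enrolled is 25 × q, where q is the share affected. With q assumed at 2% the result is 25 × 0.02 = 0.5, and at 20% it is 25 × 0.20 = 5. The documents give no value for q, so this range only restates the assumption. It also counts exposure and not harm, and it ignores any filtering by the physician. It is not evidence of severity.

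The change is worth making before enrolment because it concerns patient safety and costs little. It does not bear on the 21 evaluable or 25 enrolled patients in Sample Size.

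**What to change.** The sponsor should reconcile three places: the Exclusion Criteria, the mechanism stated in Background and Significance, and the trauma population in Subjects and Eligibility Criteria. The written bleeding-risk exclusion should also address non-GI bleeding risk that can be identified from the history and a question on current medication, for example anticoagulant use or a known bleeding disorder. The investigator should set the exact terms.

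The wording should not extend to suspected bleeding from the presenting injury. Bruising, haematoma and fracture all involve some bleeding, so an undefined item of that kind could remove much of the traumatic population that the trial intends to study.

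The cost is about one line in the Exclusion Criteria and one added question at screening. A few otherwise eligible patients would be lost and recruitment might be slightly slower. No new test is needed.

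### With one treated cohort and no comparator, a 60-minute fall of 1.3 NRS points cannot by itself be attributed to VTS-K, so the objective and hypothesis should be worded as estimation

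*Combined protocol and SAP*

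**What the plan says.** **Aim.** STUDY OBJECTIVES begins "To evaluate analgesic efficacy of orally administered VTS-K". HYPOTHESIS reads "we hypothesize that the VTS-K combination will result in analgesia with a change in pain score at least of 1.3 points on NRS", followed by "The primary outcome of this trial is the reduction in participant's pain scores at 60 minutes post medication administration".

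**Design.** The Design paragraph states "This is a prospective observational pilot trial evaluating analgesic efficacy and safety of VTS-K". Data Collection Procedures gives one regimen: "The research associate will deliver both medications (VTS-Aspirin and Oral Ketamine) to the patient". No section describes a second regimen, allocation, blinding or an external benchmark, and none limits what may be concluded about efficacy.

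**Entry and baseline.** Under STUDY DESIGN, Subjects enter "with an initial pain score of 5 or more". The Eligibility Criteria paragraph gives the score as 5, without the words for higher scores. Data Collection Procedures says "Baseline pain score will be determined with an 11-point numeric rating scale" after describing consent from patients already found eligible. It does not say whether this is a new measurement or the qualifying score carried forward.

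**Rescue.** Oral morphine is available on request to patients who still score 5 or higher. The plan does not say how scores recorded after rescue are handled.

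**Analysis and sample size.** Data Analysis names an independent-sample t-test and a difference of 1.3 between three groups, but no groups are defined anywhere. Sample Size uses a change of 1.3 from baseline to 60 minutes, SD 3.0 and a one-sided 97.5% confidence interval to reach 21 patients, raised to 25 for loss to follow-up.

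**The concern.** The objective and hypothesis are causal: they credit the before-after change to the drug. With one cohort, that change is a sum of the drug effect, the natural course of acute pain over an hour, the response to being treated openly, any rescue morphine taken before 60 minutes and, depending on which score is the baseline, regression to the mean. The design gives no means of separating these parts.

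Regression to the mean arises because patients are admitted on the same scale that measures the outcome. If the qualifying score is also the baseline, patients whose score happened to be high that moment are over-represented, and the next score tends to be lower even with an inert treatment.

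At stake is the reading of a favourable result. A mean fall of 1.3 would match the hypothesis as written, but would not show that VTS-K produced it.

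**Working it through.** **1. The plan's own figure.** Inputs from Sample Size: change 1.3, SD 3.0, one-sided 97.5% (z = 1.96).

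n = (1.96 × 3.0 / 1.3)² = 20.46, rounded up to 21. The stated figure reproduces. It is a one-sample precision formula on within-patient change, and the reference value is a change of zero. The sample size therefore agrees with the single-cohort reading and not with a comparison of three groups.

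**2. What a non-drug change does to that comparison.** Take an inert drug, SD 3.0, n = 25, and a non-drug mean change c. The values of c are assumptions; the documents give none. The standard error is 3.0/√25 = 0.6.

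| Assumed c | Chance that the lower 97.5% limit exceeds 0 (t) | Chance that the observed mean is 1.3 or more |
|---|---|---|
| 0 | 2.5% | 1.5% |
| 0.5 | 12% | 9% |
| 1.0 | 36% | 31% |
| 1.3 | 55% | 50% |

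The last column is 1 − Φ((1.3 − c)/0.6); for c = 0.5, 1 − Φ(1.33) = 9%.

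**3. Regression to the mean, if the qualifying score is the baseline.** With normal scores and entry at 5 or more (cut at 4.5 because scores are whole numbers):

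expected fall = (1 − reliability) × SD × φ(a)/(1 − Φ(a)), with a = (4.5 − mean)/SD.

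Mean, SD and reliability are assumptions about the source population; none is in the documents.

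| Mean | SD | Reliability | a | Expected fall | Share of 1.3 |
|---|---|---|---|---|---|
| 5 | 2.5 | 0.6 | −0.20 | 0.68 | 52% |
| 6 | 2.5 | 0.7 | −0.60 | 0.34 | 26% |
| 7 | 2.0 | 0.9 | −1.25 | 0.04 | 3% |

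A wider set (SD up to 3, correlation between baseline and 60 minutes down to 0.5, cut at 5) gives 0.06 to 1.2, still below 1.3.

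**4. Dependence on the entry wording.** If entry were at exactly 5, with mean 6 and reliability 0.7, the expected later score is 6 + 0.7 × (5 − 6) = 5.3, a rise of 0.3. The direction of the effect therefore depends on which of the two entry wordings is meant.

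**5. Dependence on the baseline.** If the baseline is a fresh score taken after eligibility is settled, and patients are not re-screened on it, the measurement-noise part in step 3 is about zero. Natural course, placebo response and rescue remain.

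**The case against.** The strongest reply is that the plan calls itself a pilot and observational, has 25 patients, and states a hypothesis and not a conclusion. No go/no-go rule is attached to 1.3. All of that is true, and it is why a wording change is enough. It does not remove the point, because the objective, the hypothesis and the Design paragraph are all phrased as efficacy.

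A second reply is that the order of steps in Data Collection Procedures already implies a baseline taken after eligibility. That is a fair reading, and it makes step 3 conditional. What is left there is a clarification, not a demonstrated bias. The upper end, 0.68, also needs a source mean as low as 5. The restriction to patients judged by the physician to need oral analgesia arguably points to a higher mean and a smaller effect.

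A third is that Data Analysis mentions group comparisons. Since no groups are defined, they supply no comparator.

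Two stronger readings are tempting. A reader might infer that 1.3 could be reached wholly without any drug effect. The documents do not show this: regression to the mean stays below 1.3 over the ranges tried, and no figure is given for the other components. A reader might also infer that the pilot must add a control group. A comparator is needed to show efficacy, and with the plan's own 1.3 and SD 3.0 it would take 2 × (1.96 + 0.84)² × 3.0²/1.3², about 84 per arm, for 80% power at two-sided 0.05. It is not needed for a pilot that only estimates the change.

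**Conclusion.** The point stands as a matter of what may be claimed, and should be corrected. The plan describes one cohort compared with zero change, and its causal wording goes further than that design allows. This conclusion rests on the documents alone.

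The size is less certain. Regression to the mean of about 0.04 to 0.68 points (3% to 52% of 1.3) applies only if the qualifying score doubles as baseline and entry is at 5 or more, and it uses a source mean, SD and reliability that the documents do not give. Natural course, placebo response and rescue cannot be sized from the documents. The table of chances in step 2 shows sensitivity to an assumed total; it does not estimate that total.

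**What to change.** 1. Reword the objective and hypothesis, for example: *to estimate the mean change in NRS from baseline to 60 minutes after VTS-K, with a 95% CI, to inform a controlled trial.* Add that, without a comparator, a change of 1.3 or more cannot by itself be attributed to VTS-K.
2. As a secondary clarification, state that baseline is the NRS taken after consent and before dosing, separate from the qualifying score.
3. Reconcile the two entry wordings (5, and 5 or more), and reconcile the three groups and the independent-sample t-test with the single cohort.

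No new arm or sample size is required. With SD 3.0 the 95% CI half-width is 2.064 × 3.0/√25 = 1.24 for 25 patients and 2.086 × 3.0/√21 = 1.37 for 21. The cost is wording, at most one repeat NRS question at a step the plan already has, and a more modest claim.
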